### Virology Responses

The following virology responses are also defined based on the qualitative response data:

- Anti-HBsAg seroconversion is defined as the absence of HBsAg (i.e. a 'Not Detected' result for HBsAg which is defined as a value less than 0.05 IU/mL) and the presence of Anti-HBsAg (i.e. a 'Detected' result for Anti-HBsAg). Patients will be analyzed as non-responders (seroconversion = 'No') at a specific time point if the HBsAg result at that time point is reported as equal to or greater than 0.05 IU/mL ('Detected').
- Anti-HBeAg seroconversion is defined as the change from HBeAg 'Detected' to HBeAg 'Not Detected' and the presence of anti-HBeAg (i.e. a 'Detected' result for anti-HBeAg). Patients will be analyzed as non-responders (seroconversion = 'No') at a specific time point if the HBeAg result at that time point is reported as 'Detected'. Anti-HBeAg seroconversion is only applicable to HBeAg positive patients.

For each of the response endpoints, frequent count and percentage will be summarised for each category of qualitative HBsAg, anti-HBsAg, anti-HBsAg seroconversion, HBeAg, anti-HBeAg and anti-HBeAg seroconversion response by cohort for all the assessed study visits. The exact (Clopper-Pearson) 95% confidence interval for each category (response) will be reported as well.

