4 INTRODUCTION

4.1 *Background Information*

Globally, an estimated 360 million people are chronically infected with hepatitis B virus (HBV) and up to 1 million a year die because of hepatocellular carcinoma, cirrhosis of the liver, or liver failure caused by HBV. When drug treatment is deemed appropriate, the current treatment for chronic HBV infection is a daily oral dose of nucleotide/nucleoside analogs (NUC) (depending on renal function) or a regimen of interferon injections 1 to 7 times weekly for a year or longer. Nucleotide/nucleoside analogs effectively reduce viral deoxyribonucleic acid (DNA) production by inhibiting the viral polymerase, but patients can expect to take these antivirals for life because viral replication quickly rebounds upon cessation of treatment in more than half of patients who are HBeAg (+) at baseline and more than 80% in patients who are HBeAg (-) with Chronic Hepatitis B (CHB). A more desirable outcome would be HBV surface antigen (HBsAg) loss with or without S-antigen seroconversion, which is an effective antibody response to the envelope protein that is also called HBsAg. S-antigen loss (with or without seroconversion to Anti-HBsAg) represents immune mediated viral clearance and is considered a functional cure, if HBV DNA is also undetectable. Nucleotide/nucleoside analog treatment has very little effect, if any on the level of HBsAg that is produced, nor on production of the other viral proteins. The highly abundant HBsAg produced in the infected patient, as high as 10^{12} particles/mL of blood, is believed to counteract virus-neutralizing Anti-HBsAg antibodies, allowing the virus to spread cell to cell and to be maintained in the host. The large quantities of secreted HBsAg also lead to T-cell exhaustion and anergy. Thus, even on NUC therapy, the rate of HBsAg loss in CHB patients is only about 1% annually, even after many years of NUC treatment. The rate of HBsAg clearance is similarly low from interferon treatment, and these therapeutics cause significant side effects, including severe flu-like symptoms, bone marrow suppression, and autoimmune disorders. The lack of satisfactory therapeutics for treatment of chronic HBV infection highlights the need for a different approach to this disease.

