11.6 Pharmacodynamic Data

The whole blood collected for pharmacodynamic analysis following multiple doses of ARO-HBV at different dose levels will undergo analysis for changes in HBV-DNA, HBV-RNA (if scientifically feasible) and viral antigens based on reference laboratory (VIDRL) generated values. Cellular immunologic assessments will also be conducted (if scientifically feasible) at University of Auckland.

Immunology assessments (CHB patients in New Zealand only)

- Changes in profile from pre-dose to post-dose time points for: T cell subsets (activation and exhaustion state), NK cell subsets (activation and exhaustion state), B cell subset, monocyte subsets. To be conducted if scientifically feasible.
- Changes from pre-dose to post-dose time points for: HBV antigen specific T cell response (including HBcAg, HBsAg). To be conducted if scientifically feasible.

Virology assessments (CHB patients only)

- Virologic parameters will be summarized by cohort for the following:
- Quantitative HBsAg (qHBsAg): Log change from baseline to nadir and duration of response from nadir back to approximately 20% of baseline or EOS. In CHB patients who consent to additional follow up, HBsAg will be followed until the end of the additional follow-up period or early termination and summarized separately.
- Percent of patients with loss of HBsAg (defined as quantitative HBsAg < 0.05 IU/mL) at EOS and time to occurrence (Kaplan Meier). In CHB patients who consent to additional follow up,

HBsAg loss will be monitored until the end of the additional follow-up period or early termination and summarized separately.

- Percent of patients with anti-HBS seroconversion at EOS and time to occurrence (Kaplan Meier). In CHB patients who consent to additional follow up, anti-HBS seroconversion will be monitored until the end of the additional follow-up period or early termination and summarized separately.
- Change in Anti-HBs (quantitative) to EOS. In CHB patients who consent to additional follow up, change in Anti-HBs (quantitative) will be monitored until the end of the additional follow-up period or early termination and summarized separately.
- Quantitative HBV DNA (when quantifiable at baseline): Log change from baseline to EOS. In CHB patients who consent to additional follow up, HBV DNA will be monitored until the end of the additional follow-up period or early termination and summarized separately.

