### **7.1 Demographics**

Demographic data, including age, gender, race, weight, height and BMI, will be summarized by dose level (cohort) and overall. The table will also be repeated for the subset of CHB subjects that participated in the Additional Follow-up period. A by-subject data listing for demographic characteristics will be generated.

Baseline disease characteristics including, baseline alanine aminotransferase (ALT), baseline Fibroscan score, prior nucleos(t)ide (NUC) treatment status and the type of prior treatments and the log-transformed quantitative HBV DNA, genotype (if available), qHBsAg, qHBeAg, qHBcrAg, qHBV RNA (if feasible), and anti-HBsAg values and the ratio of bound/free anti-HBs (untransformed, subset of patients only) at baseline will be summarized for the CHB cohorts as well as for the subset of CHB subjects that participated in the follow-up period. The table will also be repeated for the PD Population. A by-subject data listing for baseline disease characteristics will be generated.

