- Target Detected: All results that are equal to or above the LLQ cut-off value and results below the LLQ that have been classified as 'Detected' (for example, '<15 Detected', '< 20 Detected', etc.) by the analyzing laboratory.
- Target Not Detected: Results below the LLQ cut-off values that have been classified as 'Not Detected' by the analyzing laboratory.

The HBV RNA interpretation provided by the analyzing laboratory will be categorized as follows for the qualitative HBV RNA summary:

- Target Detected: All results where the interpretation provided by the analyzing laboratory is 'Positive' or 'LLOQ'.
- Target Not Detected: All results where the interpretation provided by the analyzing laboratory is 'Negative'.

Loss of HBsAg ('Not Detected') is defined as HBsAg of less than 0.05 IU/mL. Post-baseline qHBsAg results will be classified as follows for the qualitative HBsAg summary:

- Loss of HBsAg: Reported qHBsAg result is below the LLQ cut-off value.
- HBsAg Present: Reported qHBsAg result is equal to or above the LLQ cut-off value.

The qualitative HBeAg results will be categorized as follows for the qualitative HBeAg summary:

- Positive: Qualitative results reported as 'Detected' by the analyzing laboratory.
- Negative: Qualitative results reported as 'Not Detected' by the analyzing laboratory.

Anti-HBsAg and anti-HBeAg will be reported as 'Detected' or 'Not Detected' by the analyzing laboratory. Anti-HBsAg and anti-HBeAg will only be assessed if there was a HBsAg or HBeAg loss during the study and may not be available at all timepoints.

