### Time to Event Endpoints

- Time to HBsAg Loss is defined as the duration from first dosing to the date of HBsAg 'Not Detected' (HBsAg loss defined as HBsAg < 0.05 IU/mL). Subjects without HBsAg loss will be censored at the end of study (or the end of follow-up period).
- Time to anti-HBsAg seroconversion is defined as the duration from first dosing to the date of anti-HBsAg seroconversion. Subjects without anti-HBsAg seroconversion will be censored at the end of study (or the end of follow-up period).
- Duration of Response (for HBV DNA, qHBsAg, qHBeAg, qHBcrAg, qHBV RNA): defined as the duration from post dose nadir back to within 20% of baseline value. The analysis will only be performed for the overall study period (including the follow-up period) and only patients with baseline values above the LLQ for the specific parameter will be included in the analysis. Subjects with the endpoint not returning to within 20% of baseline value will be censored at the end of the follow-up period.

The time to event endpoints will be analyzed by survival analysis method. Survival analysis will only be conducted if there are at least some responders within a cohort. The survival functions of the time to event endpoints will be summarized for 25th percentile, median, and 75th percentile and their 95% confidence intervals. The rates of HBsAg Loss and anti-HBsAg seroconversion at Day 60 and Day 113 post dosing (and also at Days 169, 225, 281, 337 and 393 for the subset of CHB subjects that participated in the follow-up), the response rates (for HBV DNA, qHBsAg, qHBeAg, qHBcrAg, qHBV RNA) at Day 30 and Day 60 (and additional time points at 30 days intervals as appropriate) post nadir, and their respective 95% confidence intervals will be derived based on their survival functions estimated by Kaplan-Meier method. In addition, the graphs of Kaplan-Meier estimates of survival functions (survival plots) will be presented. Histograms will also be presented showing the response rates for each cohort over 30-day intervals.

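### The SAP counts antigen loss with antibody present as seroconversion, without requiring that the antibody was absent before dosing

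*SAP*

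**What the plan says.** SAP Section 11, Virology Responses, gives the anti-HBsAg rule in two parts. The antigen part reads: "Anti-HBsAg seroconversion is defined as the absence of HBsAg (i.e. a 'Not Detected' result for HBsAg". The antibody part adds that HBsAg is "less than 0.05 IU/mL) and the presence of Anti-HBsAg (i.e. a 'Detected' result for Anti-HBsAg". The only non-response rule stated is HBsAg at or above 0.05 IU/mL at that visit.

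The companion rule reads: "Anti-HBeAg seroconversion is defined as the change from HBeAg 'Detected' to HBeAg 'Not Detected' and the presence of anti-HBeAg". It requires a before-and-after change in the antigen, but not in the antibody.

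The time-to-event endpoint reuses the first rule: "Time to anti-HBsAg seroconversion is defined as the duration from first dosing to the date of anti-HBsAg seroconversion". Protocol Section 11.6 asks for "Percent of patients with anti-HBS seroconversion at EOS and time to occurrence (Kaplan Meier" and gives no definition of its own.

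Two other passages bear on baseline antibody:

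- SAP Section 7.1 says that "anti-HBsAg values and the ratio of bound/free anti-HBs (untransformed, subset of patients only) at baseline will be summarized". This baseline information does not enter the response rule.
- In its text on qualitative assessments, SAP Section 11 says that "Anti-HBsAg and anti-HBeAg will only be assessed if there was a HBsAg or HBeAg loss during the study". Protocol Tables 1.2, 1.3, 1.4 and 1.6, by contrast, schedule anti-HBs on Day 1 for every CHB patient, and anti-HBe for HBeAg-positive patients.

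**The concern.** Protocol Section 4.1 speaks of "S-antigen seroconversion, which is an effective antibody response to the envelope protein" and keeps it apart from HBsAg loss, which may come with or without it. HBsAg loss already has its own rate and Kaplan-Meier analysis. The seroconversion endpoint adds information only if the antibody is new.

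Under the SAP rule, a patient with detectable antibody on Day 1 needs only to lose the antigen to become a seroconverter. If the antibody is detected at the visit of loss, the time to seroconversion equals the time to HBsAg loss, and the second endpoint repeats the first under another name.

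The count feeds the visit-wise rate and its exact 95% interval, the Kaplan-Meier curve and the landmark rates. The SAP runs a survival analysis only where a cohort has at least some responders. In a cohort with no true seroconverter, one such patient could therefore be the reason the analysis is run at all.

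**Working it through.** The documents give no seroconversion rate or sample-size figure, so there is nothing of the plan's own to reproduce. The check is a reading of the rule, followed by an illustration of scale.

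**Step 1: apply the rule to a patient with antibody on Day 1.**

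| Condition | Day 1 | Visit after antigen loss | Required by the SAP? |
|---|---|---|---|
| HBsAg < 0.05 IU/mL | no | yes | yes, at the visit |
| Anti-HBsAg 'Detected' | yes | yes | yes, at the visit |
| Anti-HBsAg 'Not Detected' before dosing | no | – | not required |

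Both required conditions hold, so the patient is a 'Yes'. The antibody status has not changed.

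**Step 2: look for a safeguard elsewhere.** The CHB inclusion and exclusion criteria (Protocol Sections 7.2 and 7.3) set no anti-HBs condition. Inclusion requires HBsAg of at least 5 IU/mL at screening, so the antigen loss itself is a real change: log10(5/0.05) = 2, a fall of more than 2 logs. The SAP does set baseline conditions in other places; the quantitative summaries, for example, are limited to patients with a baseline result above the LLQ. None is set for antibody.

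**Step 3: scale.** Inputs are cohort sizes from SAP Section 2.4 (Cohorts 1b to 5b: 4 to 8 patients; Cohorts 6 to 11: at most 4; Cohort 12: 12) and the Clopper-Pearson interval named in SAP Section 11. Assumption: k patients in the cohort have Day 1 antibody and then lose HBsAg, and no patient truly converts. The documents do not give k, so a range is shown. Rate = k/n. For k = 0 the upper limit is 1 − 0.025^(1/n); for n = 8, 1 − 0.025^(1/8) = 36.9%.

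| n | k = 0 (also the result if Day 1 'Not Detected' is required) | k = 1 | k = 2 |
|---|---|---|---|
| 4 | 0% (0 to 60.2) | 25.0% (0.6 to 80.6) | 50.0% (6.8 to 93.2) |
| 8 | 0% (0 to 36.9) | 12.5% (0.3 to 52.7) | 25.0% (3.2 to 65.1) |
| 12 | 0% (0 to 26.5) | 8.3% (0.2 to 38.5) | 16.7% (2.1 to 48.4) |

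One such patient moves the cohort rate by 1/n: 25.0, 12.5 or 8.3 percentage points. If nobody is censored earlier, the Kaplan-Meier estimate moves by the same amount.

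**Step 4: the denominator.** The column for k = 0 keeps the patient in the denominator. Removing only those baseline-positive patients who lose the antigen would give 0/7 in a cohort of 8, with upper limit 1 − 0.025^(1/7) = 41.0%. It would also select patients on a post-baseline outcome, since baseline-positive patients without loss would stay in.

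**The case against.** The strongest case on the other side is that this is a wording matter on a descriptive endpoint. Seroconversion is not named in any primary, secondary or exploratory objective. SAP Section 2.4 says that the cohorts are too small for hypothesis testing. Every patient affected has truly lost HBsAg. Baseline anti-HBsAg is summarised and all virology data are listed by subject, so an attentive reader might spot the case.

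Much of this stands, and it keeps the point below the first rank. The listings are only a partial safeguard. If antibody is assessed only after antigen loss, the Day 1 result may be missing for the very patients who need it, and a listing does not change the count.

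A reader might infer more than the documents support:

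- **That progress towards functional cure is overstated.** Protocol Section 4.1 treats S-antigen loss as functional cure with or without seroconversion, provided HBV DNA is undetectable. Seroconversion status does not enter.
- **That the plan attributes the antibody to treatment.** The SAP makes no such claim, and the CHB cohorts are open label without a control.
- **That the plan expects antibody-positive patients at baseline.** Summarising a baseline value does not predict a positive result, and no frequency is given.

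One objection also limits the remedy. Antibody fully bound by antigen on Day 1 may read 'Not Detected', and a baseline condition would not catch it. The documents do not say whether the assay reads free or total antibody.

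**Conclusion.** The point holds as a defect in a stated counting rule. Antigen loss with antibody that was already detectable on Day 1 is reported as seroconversion, for anti-HBsAg and equally for anti-HBeAg. The bias runs one way, towards a higher seroconversion rate, and is confined to patients who lose the antigen. HBsAg loss is unaffected.

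The size depends on an unknown: how many patients have both Day 1 antibody and antigen loss. It is zero if there are none. The shifts of 25.0, 12.5 and 8.3 points assume exactly one such patient, kept in the denominator, in a cohort of 4, 8 or 12. The rule should be corrected because the endpoint cannot otherwise be read as an antibody response, but no primary conclusion rests on it.

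**What to change.** In SAP Section 11:

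1. Define seroconversion as antigen loss with antibody 'Detected' in a patient whose Day 1 pre-dose antibody was 'Not Detected'. Apply this to both anti-HBsAg and anti-HBeAg.
2. Keep every patient in the denominator and in the risk set, whatever the outcome. Those with Day 1 antibody cannot meet the event; they count as 'No' and are censored under the existing rule.
3. Show antigen loss with antibody already present on Day 1 as a separate descriptive row.
4. State that the Day 1 sample, already scheduled in Protocol Tables 1.2, 1.3, 1.4 and 1.6, is assayed for every patient with loss. This closes the gap left by assessing antibody only after loss.
5. State the limit that antibody fully bound by antigen on Day 1 may be missed, and show the baseline bound/free ratio for seroconverters where it is available.

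The cost is a few lines of SAP text and, at most, assays of samples already scheduled, in patients with antigen loss only. The downside is that the reported seroconversion rate may be slightly lower.

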### Time to Event Endpoints

- Time to HBsAg Loss is defined as the duration from first dosing to the date of HBsAg 'Not Detected' (HBsAg loss defined as HBsAg < 0.05 IU/mL). Subjects without HBsAg loss will be censored at the end of study (or the end of follow-up period).
- Time to anti-HBsAg seroconversion is defined as the duration from first dosing to the date of anti-HBsAg seroconversion. Subjects without anti-HBsAg seroconversion will be censored at the end of study (or the end of follow-up period).
- Duration of Response (for HBV DNA, qHBsAg, qHBeAg, qHBcrAg, qHBV RNA): defined as the duration from post dose nadir back to within 20% of baseline value. The analysis will only be performed for the overall study period (including the follow-up period) and only patients with baseline values above the LLQ for the specific parameter will be included in the analysis. Subjects with the endpoint not returning to within 20% of baseline value will be censored at the end of the follow-up period.

The time to event endpoints will be analyzed by survival analysis method. Survival analysis will only be conducted if there are at least some responders within a cohort. The survival functions of the time to event endpoints will be summarized for 25th percentile, median, and 75th percentile and their 95% confidence intervals. The rates of HBsAg Loss and anti-HBsAg seroconversion at Day 60 and Day 113 post dosing (and also at Days 169, 225, 281, 337 and 393 for the subset of CHB subjects that participated in the follow-up), the response rates (for HBV DNA, qHBsAg, qHBeAg, qHBcrAg, qHBV RNA) at Day 30 and Day 60 (and additional time points at 30 days intervals as appropriate) post nadir, and their respective 95% confidence intervals will be derived based on their survival functions estimated by Kaplan-Meier method. In addition, the graphs of Kaplan-Meier estimates of survival functions (survival plots) will be presented. Histograms will also be presented showing the response rates for each cohort over 30-day intervals.

All the above analyses will be conducted by CHB cohorts. In addition, separate subgroup analyses might be completed for all CHB patients receiving at least one dose, all HBeAg negative patients and all HBeAg positive patients, all treatment naïve and all entecavir or tenofovir experienced patients. As the sample size is small for each CHB cohort, the subgroup analysis might be conducted as post hoc basis, after reviewing the data from the overall 'by CHB cohort' analyses.

All virology data will be presented in the by-subject data listings. Imputed values will be flagged. Separate listings that includes only patients that had results below LLQ at baseline and that had a post-dose results above LLQ (i.e., patients that 'worsened' during the study) will be presented for all the parameters with quantitative results.

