For each CHB patient in the multi-dose cohorts the duration of the study clinic visits is approximately 25 weeks from screening to the Day 113 EOS examination. With the exception of Cohort 12 patients, all other CHB patients consenting to additional follow up will be followed as per Additional Follow-Up Schedule of Assessments (Table 1.5), every 56 days (± 5 days) for 5 additional visits after Day 113. Only Cohort 12 patients will require follow-up until the Day 337 (± 5 days) visit. Subjects consenting to additional follow up will continue on NUCs. Subjects not consenting to additional follow up will be followed per protocol based on Schedule of Assessment Tables 1.2, 1.3 and 1.4.

All CHB subjects who complete the study until Day 113 EOS examination are considered to complete the study and may continue to attend the Additional Follow-Up visits per the Schedule of Assessments (Table 1.5) if re-consent is obtained. If a subject withdraws from the Additional Follow-Up visits before the Day 337 (Cohort 12 only) or 393 visit, he or she will still be considered as a completed subject and reason for not continuing with the Additional Follow-Up visits per protocol will be recorded.

All CHB patients and NHV subjects will be contacted by phone 90 days after the EOS visit (Day 29 for NHVs and Day 113 for CHB patients) to confirm pregnancy status.

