## 11. VIROLOGY

Virology endpoints are only collected for CHB cohorts across the study period according to the protocol schedule of assessment. The analysis population for virology data is PD.

Virology endpoints will be analyzed separately for the main study (up to Day 113 EOS) and for the overall study duration, including the follow-up period, for the subset of patients that consented to participate in the follow-up. Endpoints will be derived separately for each analysis taking into consideration all the applicable data for the specific period.

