### **13. IMMUNOGENICITY**

For CHB cohorts (Cohorts 1b, 1c, 2b, 3b, 4b, 5b, 6, 7, 8, 9, 10,11 and 12) blood samples for anti-drug antibodies testing will be collected at pre-dose, day 57 and at the end of study visit (Day 113) or at early termination as per Schedule of Assessments. Anti-drug antibodies will be analyzed using the Safety Population.

Descriptive statistics will be summarised for anti-drug antibodies. For continuous antibody measurement data, the observed assay value and change from baseline (last pre-dose value on Day 1) for each dose level (cohort) for all time points assessed will be summarised descriptively. In addition to other descriptive statistics, the summary statistics will also include geometric mean in the table. If categorical data (negative/positive) are reported for antibody measurement data, these values will be summarised as well for frequent count and percentage.

All anti-drug antibodies measures will be presented in the by-subject data listings.

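### The SAP's time-to-event rules censor event-free patients at the end of study or follow-up and make no provision for patients who leave early

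*SAP*

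**What the plan says.** SAP Section 11, Time to Event Endpoints, gives three censoring rules:

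- HBsAg loss: "Subjects without HBsAg loss will be censored at the end of study (or the end of follow-up period".
- Anti-HBsAg seroconversion: "Subjects without anti-HBsAg seroconversion will be censored at the end of study (or the end of follow-up period".
- Duration of response: "Subjects with the endpoint not returning to within 20% of baseline value will be censored at the end of the follow-up period".

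None of them names the last assessment, early termination or withdrawal, and no other section supplies a rule. Rates at fixed days are then read from Kaplan-Meier curves.

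Elsewhere the documents keep these terms apart. The opening of SAP Section 11 ties the main study to Day 113: "Virology endpoints will be analyzed separately for the main study (up to Day 113 EOS". SAP Section 13 lists early termination as an alternative to the end of study: "at the end of study visit (Day 113) or at early termination as per Schedule of Assessments". Protocol 11.6 sets the limit of observation in follow-up as either of two events: "HBsAg loss will be monitored until the end of the additional follow-up period or early termination and summarized separately".

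Protocol 6.4 covers early exit from follow-up: "If a subject withdraws from the Additional Follow-Up visits before the Day 337 (Cohort 12 only) or 393 visit", then "he or she will still be considered as a completed subject". Protocol 7.4 allows replacement of patients who leave before the EOS visit for reasons other than an adverse event.

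**The concern.** These are laboratory endpoints, so a patient's status is known only up to the last sample. A Kaplan-Meier estimate needs the risk set at each event time to hold only patients still under observation. If someone last sampled at Day 57 is given a censoring time of Day 113, they enlarge the denominator for events they could not have been seen to have. In effect this fills in non-events, although SAP Section 15 rules out imputation.

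At stake are the HBsAg-loss and seroconversion rates, and the duration of response for five viral markers, by cohort. Most cohorts have 4 to 8 patients, so one patient can move an estimate by several points. SAP 2.4 says the results will be used to size later studies.

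The rule can also make two tables disagree. Visit-level percentages use patients with non-missing data as the denominator (SAP Section 3), while the Kaplan-Meier rate for the same day would count everyone.

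**Working it through.** **Inputs.** Censoring rules and estimator: SAP Section 11. Cohort sizes: SAP 2.4. The PD Population needs a baseline and at least one post-baseline assessment (SAP Section 4), so a patient who leaves after a few visits is analysed. No dropout rate is stated anywhere, so every dropout and event pattern below is an assumption.

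**The plan's own figure.** No stated figure depends on the censoring rule. The patient count reproduces: 6×4 + 6×4 + 12 = 60 and 6×8 + 6×4 + 12 = 84, taking Cohorts 6 to 11 at 4 each.

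**Direction.** The estimate is S(t) = product over event times of (1 − d/r), with d events and r patients at risk. Moving a censoring time later can only keep or raise r, so each factor, and S(t), can only stay the same or rise. For HBsAg loss and seroconversion the reported rate is 1 − S(t), which can only stay or fall. For duration of response the share still responding is S(t), which can only stay or rise.

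**Main study, cohort of 4.** One withdrawal last sampled at Day 57 and not replaced, one loss at Day 113, two others followed to Day 113.
- As written: r = 4 at Day 113, rate = 1/4 = 25.0%.
- Censored at last assessment: r = 3, rate = 1/3 = 33.3%. The Day 113 visit table would also show 1/3.

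**Follow-up, one loss at Day 281, dropouts last seen at Day 169.**

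| Cohort size | As written | Last assessment, 1 dropout | Last assessment, 2 dropouts |
|---|---|---|---|
| 4 | 1/4 = 25.0% | 1/3 = 33.3% | 1/2 = 50.0% |
| 8 | 1/8 = 12.5% | 1/7 = 14.3% | 1/6 = 16.7% |
| 12 | 1/12 = 8.3% | 1/11 = 9.1% | 1/10 = 10.0% |

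With no dropouts the two rules agree.

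**Duration of response, n = 8.** Returns at 56, 112 and 168 days after nadir, two dropouts last seen at 40 days.
- As written, share still responding at day 180: 7/8 × 6/7 × 5/6 = 5/8 = 62.5%; median not reached.
- Censored at last assessment: 5/6 × 4/5 × 3/4 = 3/6 = 50.0%; median 168 days.

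**Large-sample size.** Take exponential event and dropout times with hazards λ and δ, non-informative dropout and T = 393 days. The rule as written then estimates λ/(λ+δ) × (1 − exp(−(λ+δ)T)). For a true 20% loss and 20% dropout, λ = δ, giving 0.5 × (1 − 0.8×0.8) = 18.0%. The same formula gives 19.0% at 10% dropout and 16.9% at 30%. A true 10% becomes 9.5%, 9.0% and 8.4% at 10%, 20% and 30% dropout.

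**The case against.** The best defence is that the end of study means each patient's own exit. The rule gives no day number, the SAP is an adjunct to the protocol, and Protocol 11.6 stops observation at early termination. Quantitative HBsAg is scheduled at the early termination visit, so for a patient who attends it the exit date and last assessment coincide and the problem disappears. What stands is that the text can be read two ways. But the SAP's own usage points to Day 113, Section 13 lists early termination separately, and an exit date can still fall after the last sample. The end of follow-up is not one date either: Day 337 for Cohort 12 and Day 393 for the others.

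The practical weight is also limited. SAP 2.4 disclaims hypothesis testing, the secondary HBsAg objective is change to nadir, which this rule does not touch, and by-subject time-to-event listings are planned. Exact 95% intervals are far wider than the shift: about 1–81% for 1/4 and 1–91% for 1/3. Survival analysis is run only in cohorts with responders. The follow-up analysis covers only patients who consented to it, so those who never consented are not carried to Day 393. All of this stands and limits the importance of the point, not its direction.

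A reader might infer three stronger claims that the documents do not support:
- That the protocol expects dropouts. Protocol 6.4 is conditional and gives no rate.
- That a patient lost early is treated as never rebounding. The patient counts as not having rebounded up to the end of follow-up only.
- That the last assessment of the named parameter is the right censoring date for all three endpoints. SAP Section 11 says anti-HBsAg is assessed only after HBsAg or HBeAg loss, although the protocol's visit schedules list it routinely. If one patient in 8 seroconverts and the other seven have no post-baseline anti-HBsAg result, that rule gives 1/1 = 100%, against 1/8 = 12.5%.

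**Conclusion.** The point holds. Taken literally, all three rules keep early leavers at risk for unobserved time. Against censoring at last assessment, HBsAg-loss and seroconversion rates can only be understated and duration of response only overstated. That last-assessment censoring is itself unbiased assumes non-informative dropout.

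The size is unknown because dropout is not stated. It is zero with no dropout, 25% versus 33% in the cohort-of-4 illustration, and one to two points on a true 20% in large samples at 10–20% dropout. The analyses are descriptive. No alpha, power or sample size changes, and the secondary nadir analysis is unaffected. The change should be made, but nothing about the trial's validity turns on it.

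**What to change.** Replace the censoring sentences in SAP Section 11, Time to Event Endpoints:

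- *HBsAg loss and duration of response:* censor event-free patients at the date of their last available assessment of that parameter within the analysis period, including any early termination visit. For HBsAg loss the analysis period runs to Day 113 in the main study. For both endpoints the follow-up analysis runs to Day 337 for Cohort 12 and Day 393 for the other cohorts.
- *Anti-HBsAg seroconversion:* censor at the last assessment, within the same periods, at which seroconversion status is known. For patients without HBsAg loss that is the last HBsAg result, not the last anti-HBsAg result. This agrees with the SAP's Virology Responses rule, which already counts a patient with HBsAg of 0.05 IU/mL or more as not seroconverted.

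The cost is one sentence per definition. No new data are needed, and SAP 17.3 bases the final analysis on the final version of the SAP.
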